1.2 Study design

Study D9181C00001 is a Phase II, randomised, double-blind, placebo-controlled, parallel group, proof of concept study to evaluate the efficacy, safety, PK and immunogenicity of MEDI3506 in adult participants with uncontrolled moderate to severe asthma on standard of care.

Approximately 228 participants will be randomised in a 1:1:1 ratio to achieve 216 evaluable participants. Participants will receive **CCI** mg MEDI3506, **CCI** mg MEDI3506, or placebo **CCI** by SC injection **CCI**. The randomisation will be stratified according to sub-study participation (exploratory cough sub-study).

Participants will be enrolled in this study for up to 29 weeks. The study comprises of 3 periods including the screening period of up to 5 weeks, an intervention period of 16 weeks, and a follow-up period of 8 weeks. Details of the schedule of assessment (SoA) can be found in the clinical study protocol (CSP).

1.3 Number of participants

A sample size of 216 participants (72 participants per treatment group), randomised 1:1:1 to MEDI3506 **CC1** mg: MEDI3506 **CC1** mg: placebo, will provide at least 80% power to detect a statistically significant difference in change from baseline to Week 16 in pre-BD FEV₁, assuming a difference of 150 mL between placebo and MEDI3506, a between-participant SD of 420 mL and a one-sided- 10% alpha level. To allow for 5% participants being ineligible for the primary analysis, a total of approximately 228 participants will be randomised in the study (approximately 76/arm).

Up to 60 participants are intended to be included in the cough sub-study (approximately 20 participants per treatment group). However, given the exploratory nature of the sub-study and that it may not be activated in all countries, randomisation of participants not included in the sub-study will not be restricted, therefore, sub-study recruitment may not be achieved. Since limited data are available on cough monitoring in this population, the sub-study is considered exploratory and no formal power calculations have been performed.

2 ANALYSIS SETS

2.1 Definition of analysis sets

The following populations are defined:

Table 2 Populations for Analysis

Population/Analysis set	Description	
All Subjects	Participants who have signed the informed consent form during screening period.	
All randomised subjects	Participants who are randomised. Participants will be analysed according to their randomised treatment group.	
ITT population	Participants who are randomised and receive any study intervention. Participants will be analysed according to their randomised treatment group.	
As-treated Population	Participants who are randomised and receive any study intervention. Participants will be analysed according to the treatment they actually receive as follows:	
	Highest dose actually received at any visit	Actual arm
	0 mg MEDI3506 (Placebo)	Placebo
	> 0 mg and ≤ CC1 mg MEDI3506	CC1 mg MEDI3506
> CC1 mg MEDI3506	CC1 mg MEDI3506	

Table 2 Populations for Analysis

Population/Analysis set	Description
PK population	Participants who received at least one dose of MEDI3506 and had at least one detectable serum concentration measurement post first dose of study intervention. A participant is considered as having at least one detectable serum concentration measurement post first dose if has at least one plasma concentration that is not below the LLOQ after the first dose. Participants will be analysed according to the treatment they actually receive.
Exploratory cough sub-study	Subset of the ITT population including those participants who are participating in the exploratory cough sub-study.

ITT = Intent to treat; PK = pharmacokinetic(s).

The ITT population will be used to summarise all demographic and baseline characteristics, concomitant medications, and efficacy measures. The Exploratory cough sub-study population will be used to summarise sub-study specific efficacy measures. The As-treated population will be used to summarise all safety measures (AEs, ADA, laboratory tests, ECG, and vital signs). The PK population will be used to summarise PK measures.

2.2 Violations and deviations

The list of important protocol deviations (IPDs) is provided in the Protocol Deviation Plan (PDP).

In addition, any protocol deviation related to COVID-19 will be captured with the prefix “COVID-19” for CSR reporting.

3 PRIMARY AND SECONDARY VARIABLES

3.1 General principles

3.1.1 Baseline definitions

In general, the last measurement prior to first injection of IP will serve as the baseline measurement for efficacy and safety endpoints. If Visit 4 (Day1) measurement is missing, the last non-missing value before Visit 4 (Day 1) will be used as baseline instead. If there is no result collected prior to Visit 4, then baseline value will be set to missing and will not be imputed. In the scenario where there are two assessments on Visit 4 (Day 1) prior to first dose, one with time recorded and the other without time recorded, the one with time recorded would be selected as baseline.

An exception from the general rule will be ECGs. The mean value of each parameter from the triplicate measurements at Visit 4 (Week 0) pre-dose will be used as the baseline value.

For bi-weekly summaries, such as 2-weekly mean number of night-time awakenings, 2-weekly mean daily rescue medication usage, 2-weekly mean FEV1, 2-weekly mean PEF,

baseline would be defined as the mean from last 2 weeks (14 days) results before Visit 4 (Week 0), ie from evening of Study Day -14 to the morning of Study Day 1. If there are fewer than 10 completed days in the 14-day baseline period (where a complete day = entry from the evening AND the following morning) then baseline will be set to missing.

For CompEx analysis the mean from last 2 weeks (14 days) results before Visit 4 (Week 0) should be derived separately for morning and evening assessments. If there are fewer than 7 completed days in the 14-day baseline period (where a complete day = entry from the evening AND the following morning) then baseline for CompEx event will be set to missing. To note: PEF is expected to be collected with 3 measurements for each morning and evening assessment. The maximum value provided by the vendor (both morning and evening for the 2-weekly mean analysis and separately for the CompEx analysis) should be used to derive the baseline and any post-baseline assessments.

3.1.2 Study day

Whenever data are summarised over time, study day will be calculated based on the actual assessment date in relation to date of first IP administration.

If actual assessment date is prior to first IP administration, then study day will be:

$$\text{Study day} = \text{Actual assessment date} - \text{first IP administration date.}$$

If actual assessment date is on or after first IP administration, then study day will be:

$$\text{Study day} = \text{Actual assessment date} - \text{first IP administration date} + 1.$$

3.1.3 Absolute, relative and percent change from baseline

Absolute and percent change from baseline will be derived as follows:

$$\text{Absolute change from baseline outcome variables} = (\text{post-randomisation value} - \text{baseline value}).$$

$$\text{Percent change from baseline} = ((\text{post-randomisation value} - \text{baseline value}) / \text{baseline value}) \times 100.$$

For variables log normally distributed, the relative change from baseline is calculated as the visit log transformed value minus the baseline log transformed value.

If either the post-randomisation value or the baseline value is missing, then the changes from baseline value will also be set to missing.

Percentage change from baseline will not be calculated for participants where the result at baseline is 0.

3.1.4 Analysis visit and study phase windows

For the exacerbation and CompEx related analyses no analysis visit windows will be applied.

For PK related analyses no analysis visit windows will be applied and the actual visits and timepoints will be used instead.

Visit windows will be used for all assessments to allow for by-visit analyses, since not all assessments might be performed on the scheduled day. Unless specified otherwise, the efficacy and safety analyses will be based on the analysis visit windows. The actual assessment day will be mapped to the planned study visit following the analysis visit windowing rules below:

- If more than one assessment falls within a visit window, the closest non-missing assessment to the scheduled day will be used in the analysis.
- If more than one non-missing assessment actual dates are equidistant from the target day, the earlier assessment will be used in the analysis.
- If more than one assessment is selected (i.e. due to teste repetitions) the average for numerical values / worst case for categorical values will be used in the analysis

The visit windows for the visits following baseline are constructed in such a way that the upper limit of the interval falls half way between the two visits, rounded up to the nearest integer. The lower limit of each window will be the mean of the two adjacent planned study days +1, rounded up to the nearest integer, except for the first post-treatment visit.

Table 3 Analysis visit windows for in-clinic spirometry, FeNO, vital signs, SARS-Cov-2 PCR test, exploratory biomarkers (serum)

Protocol Visit	Week	Analysis Visit	Scheduled Study Day	Visit Window for Analysis (Days)
SV4	Week 0	Baseline	1	All assessments prior to the first administration of investigational product
SV6	Week 1	Week 1	8	All assessments on or after the first administration of investigational product to Day 19
SV7	Week 4	Week 4	29	20 to 43
SV8	Week 8	Week 8	57	44 to 71
SV9	Week 12	Week 12	85	72 to 99
SV10	Week 16	Week 16	113	100 to 127
SV11	Week 20	Week 20	141	128 to 155
SV12	Week 24	Week 24	169	≥ 156

SV = Study Visit.

For vital signs, if the selected day is a dosing day, timepoints as per SOA within the day need to be considered (ie, Baseline, Day1: post-dose, Day1: 30m, Day1: 60m, Day1: 120m, Week1, etc...).

For in-clinic spirometry pre-BD at day 1 timepoint at 4 hour post dose need also to be considered.

Table 4 Analysis visit windows for ACQ-6, haematology, coagulation parameters, serum chemistry and immunogenicity

Protocol Visit	Week	Analysis Visit	Scheduled Study Day	Visit Window for Analysis (Days)
SV4	Week 0	Baseline	1	All assessments prior to the first administration of investigational product
SV6	Week 1	Week 1	8	All assessments on or after the first administration of investigational product to Day 19
SV7	Week 4	Week 4	29	20 to 43
SV8	Week 8	Week 8	57	44 to 71
SV9	Week 12	Week 12	85	72 to 99
SV10	Week 16	Week 16	113	100 to 141
SV12	Week 24	Week 24	169	≥142

SV = Study Visit.

Table 5 Analysis visit windows for SNOT-22, Airwave Oscillometry and urinalysis

Protocol Visit	Week	Analysis Visit	Scheduled Study Day	Visit Window for Analysis (Days)
SV4	Week 0	Baseline	1	All assessments prior to the first administration of investigational product
SV6	Week 1	Week 1	8	All assessments on or after the first administration of investigational product to Day 19
SV7	Week 4	Week 4	29	20 to 43
SV8	Week 8	Week 8	57	44 to 71
SV9	Week 12	Week 12	85	72 to 99
SV10	Week 16	Week 16	113	≥100

SV = Study Visit.

Table 6 Analysis visit windows for SGRQ

Protocol Visit	Week	Analysis Visit	Scheduled Study Day	Visit Window for Analysis (Days)
SV4	Week 0	Baseline	1	All assessments prior to the first administration of investigational product
SV7	Week 4	Week 4	29	All assessments on or after the first administration of investigational product to Day 57
SV9	Week 12	Week 12	85	58 to 99
SV10	Week 16	Week 16	113	100 to 141
SV12	Week 24	Week 24	169	≥142

SV = Study Visit.

Table 7 Analysis visit windows for NT-proBNP assessment

Protocol Visit	Week	Analysis Visit	Scheduled Study Day	Visit Window for Analysis (Days)
SV4	Week 0	Baseline		All assessments prior to the first administration of investigational product
SV8	Week 8	Week 8	57	All assessments on or after the first administration of investigational product to Day 71
SV9	Week 12	Week 12	85	72 to 99
SV10	Week 16	Week 16	113	100 to 141
SV12	Week 24	Week 24	169	≥142

SV = Study Visit.

Table 8 Analysis visit windows for ECGs and total IgE (serum)

Protocol Visit	Week	Analysis Visit	Scheduled Study Day	Visit Window for Analysis (Days)
SV4	Week 0	Baseline	1	All assessments prior to the first administration of investigational product
SV10	Week 16	Week 16	113	All assessments on or after the first administration of investigational product to Day 141
SV12	Week 24	Week 24	169	≥142

SV = Study Visit.

Table 9 Analysis visit windows for PGI-BR, SARS-Cov-2 serology testing, sST2 (serum), nasal mucosal sampling (mRNA), at-home cough monitoring and cough VAS

Protocol Visit	Week	Analysis Visit	Scheduled Study Day	Visit Window for Analysis (Days)
SV4	Week 0	Baseline	1	All assessments prior to the first administration of investigational product
SV10	Week 16	Week 16	113	All assessments on or after the first administration of investigational product

SV = Study Visit.

Table 10 Analysis visit windows for echocardiogram

Protocol Visit	Week	Analysis Visit	Scheduled Study Day	Visit Window for Analysis (Days)
SV4	Week 0	Baseline	1	All assessments prior to the first administration of investigational product
SV9	Week 12	Week 12	85	All assessments on or after the first administration of investigational product

SV = Study Visit.

Table 11 Analysis visit windows for EDN (plasma)

Protocol Visit	Week	Analysis Visit	Scheduled Study Day	Visit Window for Analysis (Days)
SV4	Week 0	Baseline	1	All assessments prior to the first administration of investigational product
SV7	Week 4	Week 4	29	All assessments on or after the first administration of investigational product to Day 71
SV10	Week 16	Week 16	113	72 to 141
SV12	Week 24	Week 24	169	≥142

SV = Study Visit.

Table 12 Analysis visit windows for nasal mucosal sampling (lining fluid)

Protocol Visit	Week	Analysis Visit	Scheduled Study Day	Visit Window for Analysis (Days)
SV4	Week 0	Baseline	1	All assessments prior to the first administration of investigational product

Protocol Visit	Week	Analysis Visit	Scheduled Study Day	Visit Window for Analysis (Days)
SV7	Week 4	Week 4	29	All assessments on or after the first administration of investigational product to Day 43
SV8	Week 8	Week 8	57	44 to 71
SV9	Week 12	Week 12	85	72 to 99
SV10	Week 16	Week 16	113	100 to 127
SV11	Week 20	Week 20	141	128 to 155
SV12	Week 24	Week 24	169	≥ 156

SV = Study Visit.

Daily at-home eDiary (e.g., PEF, pre-BD FEV1, FEV1, rescue medication usage, asthma symptom score, awakenings) will primarily be summarised and analysed as 2-weekly averages, separately. The assessment period of visit windows are defined in the below table.

Table 1 Labelling of 2-weekly periods

2-weekly period	Adjusted defined windows visit	Scheduled day
Baseline: as defined in Section 3.1.1	Baseline	1
Period 1: Evening of Day 1 – Morning of Day 15	Week 2	15
Period 2: Evening of Day 15 – Morning of Day 29	Week 4	29
Period 3: Evening of Day 29 – Morning of Day 43	Week 6	43
Period 4: Evening of Day 43 – Morning of Day 57	Week 8	57
Period 5: Evening of Day 57 – Morning of Day 71	Week 10	71
Period 6: Evening of Day 71 – Morning of Day 85	Week 12	85
Period 7: Evening of Day 85 – Morning of Day 99	Week 14	99
Period 8: Evening of Day 99 – Morning of Day 113	Week 16	113
Period 9: Evening of Day 113 – Morning of Day 127	Week 18	127
Period 10: Evening of Day 127 – Morning of Day 141	Week 20	141
Period 11: Evening of Day 141 – Morning of Day 155	Week 22	155
Period 12: Evening of Day 155 – Morning of Day 169	Week 24	169

The Early Discontinuation and unscheduled visits will be included when applying the visit windows to ensure that all available data are used in the analysis.

For bi-weekly summaries, the mean of all non-missing observations within an assigned window is calculated. If there are fewer than 10 completed days in the 14 day period (where a

complete day = entry from the evening AND the following morning) then the analysis value will be set to missing.

Finally, for the purpose of the statistical analysis, the assessments will be allocated to the study phase in which they are collected as reported below.

Table 2 Study phase windows

Study phase	Phase Window for Analysis (Days)
Pre-treatment	Prior to the first administration of investigational product (day <1 ^a)
On-treatment	≥ day 1 ^b to last dose date plus 28 days (included)
Follow-up	> last dose date plus 28 days

^a Includes all measurements collected before first dose of IP. If the measurement is collected on day 1 it cannot be determined if it was done before or after the first dose of IP (due to missing time and/or planned time point), then it will be considered as collected after first dose of IP.

^b Includes all measurements collected on the day of first dose of IP, at the time of IP intake and after.

Unless otherwise specified, the study phase will be mainly used for safety analysis (e.g., laboratories, adverse events) and for CompEx analysis.

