^e Echocardiogram and NT-proBNP assessments also to be performed as required, for participants who might be experiencing heart failure, or as soon as possible after heart failure might have occurred.

^f May be performed at any time at or between SV9 (Week 12) and SV10 (Week 16) inclusive.

^g Testing may be performed at any point for a participant suspected of having COVID-19.

^h Prior to administration of study intervention on days when study intervention is administered.

Table 2 Schedule of Activities: Study Intervention and Follow-up Periods

Period	Study Intervention							Follow-up		E/D
Visit Number	SV4 (Random- isation)	SV5 (TC)	SV6	SV7	SV8	SV9	SV10	SV11	SV12	
Study Day	1	2	8 (± 3)	29 (± 3)	57 (± 3)	85 (± 3)	113 (± 3)	141 (± 3)	169 (± 3)	
Study Week	0	0	1	4	8	12	16	20	24	

ⁱ If not performed at SV4, can be performed at any subsequent visit. As a last resort if the participant has completed the study (and not withdrawn consent) but the sample has not been received by the analysing laboratory, the site should ask the participant if he/she would be willing to attend an additional optional visit to provide this sample.

^j Female participants of childbearing potential only.

^k If deemed by investigator to be intolerable for individual participant at SV4 (eg, due to nasal polyps), subsequent assessments may be omitted. If this assessment is not performed at SV4 for any reason, it should not be repeated at SV10.

^l Participants should be monitored for a minimum of one to 2 hours after administration of study intervention (see Section 8.2.3). If a suspected anaphylactic reaction occurs during or within a 24-hour period after administration of study intervention, blood samples for serum tryptase will be collected as soon as possible after the event, at 60 ± 30 minutes after the event, at discharge, and between 2 and 4 weeks post-discharge. Immediate care of the participant and treatment of the reaction must take priority over collecting blood samples. Additional details on anaphylactic reactions are provided in Appendix G and Appendix H.

^m For COVID-19 mitigation, please see Section 2.3.1.2.

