4.2.7.5 Analysis of echocardiogram

Observed values and change from baseline in LVEF will be summarised by visit, by treatment group and for total MEDI3506 using descriptive summary statistics for the As-treated population.

Individual echocardiogram results and abnormalities will be listed.

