4.2.7.6 Other safety tests

NT-proBNP results will be summarised with descriptive statistics at each visit and change from baseline summarised for each post-baseline visit for the As-treated population. NT-proBNP results will be also summarised in shift tables comparing maximum value during treatment with baseline value for the As-treated population.

The number of subjects tested positive for SARS-CoV-2 (by PCR or serology test) at end of study, but who were tested negative at baseline visit will also be presented.

Finally, the number of subjects tested positive for SARS-CoV-2 (by PCR or serology test) during the study (including both intervention and follow-up periods) who experienced or not at least one COVID-19 related AEs/SAEs will be provided.

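### When a participant has both a scheduled and a for-cause echocardiogram, the by-arm LVEF table keeps only the reading nearest Day 85, so the lowest LVEF across all echocardiograms is not compared by arm

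*SAP*

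**What the plan says.** Protocol Table 3 names progression of heart failure as a potential risk and lists echocardiogram and NT-proBNP monitoring among the mitigations. LVEF is a safety endpoint for the intervention and follow-up periods (Protocol Section 3; SAP 1.1).

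One post-baseline echocardiogram is scheduled, at any time from SV9 (Week 12) to SV10 (Week 16). Footnote e to Protocol Table 2 adds others: "Echocardiogram and NT-proBNP assessments also to be performed as required, for participants who might be experiencing heart failure".

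The SAP handles these readings as follows.

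- The table headed "Analysis visit windows for echocardiogram" (SAP 3.1.4, Table 10) has a baseline row and one post-baseline row, Week 12, scheduled Day 85. That row starts at first dose and has no upper limit.
- Within a window, "If more than one assessment falls within a visit window, the closest non-missing assessment to the scheduled day will be used in the analysis". For ties, "If more than one non-missing assessment actual dates are equidistant from the target day, the earlier assessment will be used in the analysis". If several readings are still selected, "the average for numerical values / worst case for categorical values will be used in the analysis".
- Early discontinuation and unscheduled visits enter the windows, with the stated aim "to ensure that all available data are used in the analysis".
- SAP 4.2.7.5 plans one kind of LVEF summary: "Observed values and change from baseline in LVEF will be summarised by visit", by treatment group and for total MEDI3506. The output list has one LVEF table (14.3.8.3). All echocardiogram results and abnormalities are listed.
- For the companion marker, SAP 4.2.7.6 adds an extreme-value output: "NT-proBNP results will be also summarised in shift tables comparing maximum value during treatment".

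**The concern.** Safety analyses follow the visit windows unless the SAP says otherwise, and it makes no exception for LVEF. A scan prompted by suspected heart failure therefore competes with the routine scan for a single slot. Closeness to Day 85 decides which is used, whatever the LVEF value. SAP 3.5.5 describes only the screening and SV9-to-SV10 echocardiograms, which suggests that the extra scans were not considered when the window was drawn.

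Two things can happen. A low for-cause reading may be left out of the table because a later routine reading lies nearer Day 85. Or the for-cause reading may take the slot, so that a row labelled Week 12 mixes routine and symptom-prompted scans. In either case the lowest measured LVEF of participants with extra scans is not reliably compared between arms. These are the participants for whom the protocol asks for the extra measurement.

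**Working it through.** The plan gives no figure to reproduce here. The check applies the selection rule literally to participants who have both scans.

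**Inputs**

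- Target day: 85 (SAP Table 10).
- Scheduled scan day *s*: SV9 is Day 85 ± 3 and SV10 is Day 113 ± 3 (Protocol Table 2), so *s* runs from 82 to 116.
- For-cause scan day *h*: not given in the documents. I assume Days 2 to 169 (168 days, SV12 being nominal Day 169) with even spread, and then vary this.

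**Rule**

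- Keep *h* if |*h* − 85| < |*s* − 85|.
- Keep *s* if |*h* − 85| > |*s* − 85|.
- If the distances are equal on different days, keep the earlier.
- If *h* = *s*, average the two.

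**Single cases**

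- *h* = 30: distance 55. Against *s* = 85 (distance 0) or *s* = 113 (distance 28), the for-cause reading is dropped.
- *h* = 60: distance 25. Against *s* = 113 (28), it replaces the scheduled reading. Against *s* = 85 (0), it is dropped.
- *h* = 130: distance 45. It is dropped against either.

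**Share of for-cause days dropped, even spread over Days 2 to 169**

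| Scheduled day | For-cause days kept | Averaged | For-cause days dropped | Share dropped |
|---|---|---|---|---|
| 85 | none | Day 85 | 2–84 (83) and 86–169 (84) = 167 | 167/168 = 99% |
| 113 | 57–112 (56) | Day 113 | 2–56 (55) and 114–169 (56) = 111 | 111/168 = 66% |
| 116 | 54–115 (62) | Day 116 | 2–53 (52) and 117–169 (53) = 105 | 105/168 = 62.5%, about 63% |

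Averaging the same count over every scheduled day from 82 to 116 gives 82%.

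**Sensitivity to the timing assumption**

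- For-cause scans on Days 2 to 116 only, scheduled Day 116: Days 2–53 are dropped, 52/115 = 45%.
- For-cause scans on Days 57 to 113 only, scheduled Day 113: Days 57–112 are kept and Day 113 is averaged, so 0% are dropped. With scheduled Day 116, all are kept.

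Where the for-cause reading is kept on a different day, the scheduled reading is the one lost.

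**Participants with only one post-baseline scan.** If the for-cause reading is the only one after first dose, it is kept whatever its date.

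**The case against.** The strongest reply is that the effect is narrow and the safety signal has other routes into the report. Several parts of it stand.

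- **The table is not limited to means.** SAP 4.1 defines the standard descriptive statistics to include minimum and maximum. The lowest selected LVEF and the largest selected fall will be shown by arm. Only unselected readings are missing.
- **Both scans are needed for a loss.** Protocol 7.1 stops study intervention on confirmed heart failure, and Protocol Table 2 has no echocardiogram in the early-discontinuation column. A participant who leaves the study before SV9 may have only the for-cause reading, which is then kept. One who stops treatment but stays in the study may still have the scheduled scan.
- **Heart-failure events are tabulated elsewhere.** Adverse events by system organ class and preferred term, serious adverse events and adverse events of special interest (which include congestive heart failure) are summarised by arm (SAP 4.2.7.1). NT-proBNP has its maximum-value shift table. The DSMB reviews unblinded safety data, and Protocol 4.4.1 allows a hold after two or more echocardiographically confirmed reports of new symptomatic heart failure.

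A reader might therefore infer that the plan hides a heart-failure signal, or that most for-cause readings will be lost. The documents support neither. The events have by-arm tables, every echocardiogram is listed, and no timing or number of for-cause scans is given.

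Two further replies carry less weight. With only one scheduled post-baseline scan, a lowest-value table would match a scheduled-scan table except for participants with extra scans. That is true, but those are the participants at issue. A minimum also depends on how often someone is scanned, and scans are read locally (Protocol 8.2.5). That is a real caveat, and it is met by showing scan counts.

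**Conclusion.** The point holds in limited form. For participants with both a scheduled and a for-cause echocardiogram on different days, the SAP uses one LVEF and discards the other according to distance from Day 85. As a result, the lowest LVEF across all echocardiograms is not compared by arm, and unselected readings appear only in listings. This also falls short of the SAP's own aim of using all available data.

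The existence of the loss follows from the text. Its size does not. About 63% (scheduled Day 116) to 99% (scheduled Day 85) rests on even spread of for-cause scans over Days 2 to 169 and on both scans being present. It is a share of possible days, not a forecast of scans, and other timings take it down to 0%. The effect is confined to the LVEF summary: event tables, sample size, power and the primary analysis are untouched. It is worth correcting because LVEF is the measured endpoint for a named risk and the correction is cheap.

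**What to change.** In SAP 4.2.7.5:

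1. Restrict the by-visit LVEF table to the scheduled SV9-to-SV10 echocardiogram, so that the row has one meaning.
2. Add one table, by arm and for total MEDI3506, of each participant's lowest post-baseline LVEF from all scheduled and unscheduled echocardiograms through end of study. Include its change from baseline and the number (%) below 45%. That value is the protocol's own entry limit (exclusion criterion 6) and would serve here only as a descriptive cut-off.
3. In the same table, show the number of echocardiograms per arm, because more scans give more chances of a low value.

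The cost is one extra table and a sentence of SAP text, using data already collected. Under the added table every for-cause reading enters the by-arm comparison. The drawback is the dependence on scanning frequency, which item 3 makes visible but does not remove.
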